The proposed project, developed in partnership with CareSource, tests the effectiveness and cost-effectiveness of using their Jail-Medicaid data system as a suicide prevention tool to: (1) identify jail releases (an indicator of person-level and temporal suicide risk); and (2) trigger suicide prevention activities. Evidence-based suicide prevention practices to be used were chosen in close collaboration with CareSource, who will be providing and/or funding them. Guiding principles in choosing interventions and study design included research evidence, scalability (to 43,000 Ohio subscribers passing through jail annually), and CareSource needs, constraints, and ongoing initiatives. Involving end-users intimately in study and intervention design, as we have done in this proposal, helps shorten the research-to-practice pipeline.⁴⁴

C. Experimental Method

The following sections summarize the methods for the study components of Study 1 (Caring Contacts) and Study 2 (Reports, Re-engagement, and Training). Each section will be broken down into the following subsections:

1. Study 1 (Caring Contacts [CC])
 - a. Focus Groups
 - i. Provider focus groups
 - ii. Subscriber focus groups
 - b. CC letters
2. Study 2 (Reports, Re-engagement, and Training [RRT])
 - a. RRT Intervention
 - b. Provider meetings

For clarity, there are three types of groups that will be convened over the course of the study to gather information related to study-relevant topics:

- The first pertain to focus groups (including providers and CareSource subscribers) that will be used to (a) design and (b) provide feedback on revisions of the CC letter to be mailed by CareSource. These are referred to as focus groups in this protocol;
- The second are provider meetings where providers who have consented to participate in the RRT intervention will be asked to meet monthly with the Study PIs and CareSource to talk about their experiences, offer feedback, and help problem-solve challenges. These are referred to as provider meetings in this protocol; and
- The third will include stakeholders (e.g., individuals with lived jail experience, providers) will provide feedback on the intervention to improve scalability, sustainability, feasibility, acceptability, and appropriateness. The recruitment and processes for this third group will be part of the larger P50 Center's Methods Core and will be covered under the Center's IRB.

C1. Brief Description of Subjects

Study 1 (Caring Contacts)

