RRT Fidelity. We will be able to electronically track whether reports go out and whether they are timely/accurate. In addition, although we do not have a scalable way to track outreach attempts for 6,000 subscribers in Study 2, we will carefully document implementation processes and meet monthly with CareSource and intervention agencies, hear their experiences, offer feedback, and help problem-solve challenges. We will keep structured implementation process notes from these meetings for further analysis. Provider names will be included in the notes. All data from the implementation process feedback will be securely stored in REDCap. No names or identifiers will be used in any published works and will be accessible only to authorized research staff. Testing our service engagement mechanism will also help to elucidate steps in the causal chain (i.e., from the reports, to services provided, to suicide attempts).

Assignment to “intervention” and “control” conditions in the two studies is independent: participants may receive Intervention-Intervention, Intervention-Control, Control-Intervention, or Control-Control. Participants will be followed for 6 months following jail release using claims data.

C4. Data Analysis

Twelve months of historical (i.e., prior to arrest) and six months of prospective (i.e., after release) jail and Medicaid claims data will be extracted from CareSource’s Jail-Medicaid database for each participating subscriber for all measures, including demographics, diagnoses, suicide attempts, service use, number of arrests, dates of jail bookings/releases, and days incarcerated. Each eligible subscriber will be followed for 6 months following the index release from jail using claims data. CareSource will provide a limited dataset to the P50 Center (at MSU) that will be de-identified and analyzed by Center statisticians. Because these statisticians are employed by Brown University, an IAA will be established with both MSU and Brown University.

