
score,⁶¹⁻⁶² and per capita incarceration (by zip code) as moderators of intervention effects on suicide attempts, using $p < .01$.

Aim 2 will be analyzed by examining the number of outpatient BH claims in the 6 months following the index jail release and number of calls to the CMS line as mediators of the intervention/s effects on suicide attempts by adding this variable to our effectiveness model. Mediation is revealed by the extent to which the intervention effect parameter estimates change with the addition of the putative mediator. We will use bootstrap methods to estimate 95% uncertainty intervals around the mediated effect.

For Aim 3, our grants accounting will capture the costs of the CC mailings. Treatment received as part of the intervention and CAU conditions (including outpatient, inpatient, and ED mental health and suicide-related medical care visits) will be tracked using claims data. Costs of CAU will be computed as CareSource payments plus co-pay and deductibles. We will add training costs for providers but exclude other research costs that would not be incurred if RRT was standard care. The primary cost-effectiveness (CE) measure, computed from a societal perspective for each intervention arm, will be the program cost divided by the sum of suicide attempts prevented. We also will assess the net cost of the program from a MCO perspective. That measure will exclude patient payments from costs.

Costs (and savings) in future years will be discounted to present value in the year of jail release using the 3% discount rate recommended by the Second Panel on Cost-Effectiveness in Health and Medicine.⁶³ We will bootstrap the 95% uncertainty interval around the CE ratio. Analyses from the MCO perspective will compute the change in claims costs by running a generalized linear model (GLM) with gamma, inverse Gaussian, or Poisson variance based on data distribution, the log link function, and robust standard errors.⁶⁴ We will use a 2-part GLM unless less than 5% of patients have zero costs. Independent variables will include treatments received, demographics, Elixhauser co-morbidities,⁶⁵ and days of MCO coverage after jail discharge. We also will track the MCO separation rate post-discharge by group.

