Subscriber focus groups: Subscribers who participate in a focus group will be compensated \$50.

CC letters: No patients will be followed prospectively through any direct means of engagement, so no material inducements will be provided to study participants.

Study 2

RRT Intervention: Providers will be offered the opportunity to earn continuing education credits following completion of the required study trainings.

Site interviews and Provider meetings: No material inducements will be provided for involvement in the site interviews or provider meetings. As noted above, providers will complete study-related procedures during work time and are typically not able to accept material inducements.

E. Training of Research Personnel

All research personnel will receive training in research ethics. Research personnel will complete the Collaborative Institutional Training Initiative (CITI Program) on Human Subjects Research.

3) Human Subjects

A. Subject Population

Human subjects in this study include (1) Focus group participants (BH providers and CareSource subscribers), (2) BH providers participating in the RRT Intervention, and (3) the ~43,000 Ohio CareSource subscribers who pass through jails over 12 months. However, because our research will only use de-identified claims data from the individuals in #3, their involvement does not meet criteria for human subjects research and they are not considered participants in this study, even though they may be randomized to receive an intervention intended to reduce suicide outcomes. All participants will be 18 years of age or older.

For the Focus groups in Study 1 (Caring Contacts), there will be up to 5 total focus groups: 2 with CareSource providers and up to 3 with CareSource subscribers who have spent time in jail. Each of the focus groups may have up to 10 participants (up to 10 participants per focus group x up to 5 focus groups = ~50 potential focus group participants).

We plan to randomize approximately 43,000 Ohio CareSource subscribers who pass through jails over 12 months to receive either Caring Contact letters sent by CareSource or Care as Usual. In Study 2, we will include a subset of those subscribers (approximately 6,000) who have also been seen at one of the 12 largest behavioral health agencies in Ohio in the 6 months prior to their jail detention.

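### Aim 3 names no cost source for CareSource's own delivery inputs or for agency outreach time, so cost per attempt prevented risks being understated, chiefly for RRT

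*Combined protocol and SAP*

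**What the plan says.** The Aim 3 paragraphs of C4 Data Analysis name three cost sources.

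- **CC mailings:** "our grants accounting will capture the costs of the CC mailings".
- **Treatment:** "Treatment received as part of the intervention and CAU conditions" is tracked through claims, covering outpatient, inpatient and emergency care.
- **RRT:** "We will add training costs for providers but exclude other research costs that would not be incurred if RRT was standard care".

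The primary measure, "computed from a societal perspective for each intervention arm, will be the program cost divided by the sum of suicide attempts prevented", is not broken into components. A second measure takes the managed care organization (MCO) perspective and drops patient payments; its stated analysis models the change in claims costs.

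Three other sections bear on who supplies the resources.

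- B. Background says the practices "were chosen in close collaboration with CareSource, who will be providing and/or funding them".
- C2 Study Design has CareSource mail the letters, answer the care management service (CMS) line named in them, and generate the weekly reports to agencies.
- C2, under RRT Fidelity, says "we do not have a scalable way to track outreach attempts for 6,000 subscribers in Study 2". D. Material Inducements adds that "providers will complete study-related procedures during work time".

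**The concern.** A societal ratio should count the resources used to deliver a program, whoever pays for them. Two groups of inputs have no named source.

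- **CareSource's incremental inputs:** handling the CMS-line calls that the letters invite, producing the weekly reports, and any mailing cost the grant does not pay.
- **Agency time:** acting on the reports and reaching released clients. This is the recurring work that RRT asks of providers, and it falls in paid working time.

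Leaving out a real delivery input lowers the numerator and so, other things equal, the cost per attempt prevented. The two perspectives are affected differently. Unbilled agency time matters to the societal ratio but is not a cost to the MCO. CareSource's staff and system time matters to both; if it is omitted, the MCO's return on investment is overstated. Aim 3 promises cost-effectiveness and return on investment, and the project targets scalability, so a prospective adopter would look to these figures.

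The gap is hard to close afterwards. Claims can be re-extracted, but if outreach is neither counted nor timed, nothing remains from which to cost it.

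**Working it through.** The plan states no program cost, unit cost, outreach time or expected ratio, so there is no figure to reproduce. The check sets inputs against sources, then illustrates scale.

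**Delivery inputs and named cost sources**

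| Input | Source named in the plan |
|---|---|
| CC mailings | Grant accounting |
| Provider training (RRT) | Added; source not detailed |
| Billed treatment | Claims; role in program cost not stated |
| CMS-line call handling | None (calls are counted as an outcome) |
| Weekly-report production | None |
| Mailing cost outside the grant, if any | None |
| Agency time on reports and outreach | None |

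**RRT labour**

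1. Training hours (C1 and C2): 120 providers, 6 h for safety planning and C-SSRS, 0.5 h for re-engagement, and a 2.5 h fidelity session that may or may not lie inside the 6 h. 120 x 6.5 = 780 h; 120 x 9 = 1,080 h.
2. Exposed releases: cohorts start at Months 4, 6, 8 and 10. Assume equal-sized cohorts, releases spread evenly over 12 months, and one index release per subscriber. Exposed share = mean of (13 - start)/12 = (9 + 7 + 5 + 3)/48 = 0.50; 6,000 x 0.50 = 3,000.
3. Outreach time is an assumption, since the documents give none: 0.25 to 2 h of incremental time per exposed release.

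| Assumed h per release | Outreach hours | (Training + outreach) / training, 1,080 h base | Same, 780 h base |
|---|---|---|---|
| 0.25 | 750 | 1.7 | 2.0 |
| 0.5 | 1,500 | 2.4 | 2.9 |
| 1 | 3,000 | 3.8 | 4.8 |
| 2 | 6,000 | 6.6 | 8.7 |

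4. Per attempt prevented, using the plan's planning values (six-month risk 0.05, OR 0.87): p1 = 0.05 x 0.87 / (0.95 + 0.05 x 0.87) = 0.04378. Attempts prevented = 3,000 x (0.05 - 0.04378) = 18.6 (unrounded p1). Outreach is then 750/18.6 to 6,000/18.6, about 40 to 322 h per attempt prevented.

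**CC mailings, if any part falls outside the grant**

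5. Letters: 21,500 x 6 = 129,000 if all are sent. With OR 0.89, p1 = 0.05 x 0.89 / (0.95 + 0.05 x 0.89) = 0.04475. Attempts prevented = 21,500 x (0.05 - 0.04475) = 113 (unrounded p1). Each $1 per letter not captured would add 129,000/113, about $1,142 per attempt prevented. If the grant pays for all mailings, this term is zero.

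**The case against.** A reader might infer more than the documents support, in five ways.

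- **That only grant accounting and training are counted.** Claims are a third source. Billed re-engagement visits, and any risk assessment or safety planning within them, may be visible there. What is missing is a statement of whether they enter program cost.
- **That outreach time is declared untracked or excluded.** The tracking sentence concerns outreach attempts, in a fidelity context. The exclusion covers research costs that routine RRT would not incur; outreach and reports are not of that kind. The plan is silent on them and does not set them to zero. Structured meeting notes and process mapping are also planned, but nothing says they will record time or cost.
- **That CareSource's role proves the mailing cost incomplete.** Providing and/or funding the interventions is compatible with the grant paying for every letter. The CMS-line and report-production gaps would remain.
- **That the ratios will be too favourable.** As written, the primary measure does not net out averted care costs, which pulls the other way, and the documents size neither effect. Only the direction of the omission, other things equal, is established.
- **That the multiplier estimates the error.** It treats trainee hours as the only labour counted, prices all hours alike, assumes every exposed release is worked, and ignores trainer cost and claims-costed visits. D3 Data Safety Monitoring Plan describes reaching out after jail release as standard of care, so incremental time is below gross time. That outreach goes unbilled is itself an assumption.

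These points stand and limit the claim to a risk of understatement. They do not supply a source for the uncosted inputs.

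**Conclusion.** The point holds as a gap in the costing plan. The societal ratio has an unitemised numerator, and recurring delivery inputs have no named source. Cost per attempt prevented risks being understated, chiefly for RRT, and MCO return on investment risks being overstated to the extent that CareSource's own delivery costs are omitted.

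The true size cannot be computed from the documents. The range of 1.7 to 8.7 times training labour rests on the assumed 0.25-2 h and about 3,000 exposed releases, and shrinks where outreach is already usual care or is billed. It shows that the omitted input could rival or exceed the one that is named. The Aim 1 effectiveness analyses are unaffected.

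**What to change.** 1. List the components of program cost for each intervention, with a data source for each, and state whether claims-based treatment enters the numerator.
2. Ask CareSource for its incremental mailing, report-production and CMS-line costs. Value the CMS calls already counted as an outcome.
3. Estimate incremental outreach time per released client from a brief sampled question or log at the existing monthly provider meetings. If that is not feasible, use a stated assumed range. Value the time at wage rates.
4. Report the ratio with a sensitivity range on outreach time. Treat the jail-data feed, which existed before the trial, as a sensitivity item and not a base-case cost.

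The cost is one request to CareSource, a small amount of added data collection from providers and possibly a minor protocol amendment. The ratios are likely to look less favourable.

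### The primary societal cost-effectiveness ratio has an undefined numerator that, read literally, is neither incremental to usual care nor net of induced and averted treatment

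*Combined protocol and SAP*

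**What the plan says.** All the relevant text is in the Aim 3 paragraphs of section 2.C4 (Data Analysis).

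- **Primary measure.** It is "computed from a societal perspective for each intervention arm, will be the program cost divided by the sum of suicide attempts prevented".
- **Secondary measure.** "We also will assess the net cost of the program from a MCO perspective". Of this measure the plan adds: "That measure will exclude patient payments from costs".
- **Cost inputs.** For Caring Contacts (CC), "our grants accounting will capture the costs of the CC mailings". For RRT, "We will add training costs for providers but exclude other research costs that would not be incurred if RRT was standard care". For care use, "Treatment received as part of the intervention and CAU conditions (including outpatient, inpatient, and ED mental health and suicide-related medical care visits) will be tracked" through claims. For the comparator, "Costs of CAU will be computed as CareSource payments plus co-pay and deductibles".
- **Savings.** They appear in the discounting sentence: "Costs (and savings) in future years will be discounted to present value in the year of jail release".
- **Model for change in claims costs.** A log-link generalized linear model, in two parts unless few patients have zero cost, is assigned to the MCO perspective. Its listed covariates are treatments received, demographics, comorbidities and days of MCO coverage.
- **Uncertainty.** The interval for the cost-effectiveness ratio is to be bootstrapped.

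The term program cost is not defined anywhere in the document.

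**The concern.** A societal ratio normally compares intervention with usual care on all the costs that differ between them. Here the measure with the broader label has the narrower stated numerator, and the netting is written only for the narrower MCO perspective.

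This matters because both interventions work through care use. Section 2.C2 has RRT providers re-engaging clients in services, and CC letters reminding recipients how to reach care. Aim 2 tests outpatient behavioral health claims and calls to the care management line as mediators. The plan does not predict that outpatient use will rise; that is an inference from the re-engagement design and the mediation hypothesis. If it does rise, and attempts fall, outpatient payments go up and payments for treating attempts go down. A numerator of mailing or training cost alone would register neither, so the ratio could be too low or too high, and its label would promise more than the formula delivers.

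**Working it through.** The plan states no cost, saving or ratio, so there is no figure of its own to reproduce. The check has two parts.

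**1. The text side by side**

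| Element | Primary (societal) | Secondary (MCO) |
|---|---|---|
| Numerator as worded | program cost | net cost of the program |
| Model for change in claims costs | none stated | generalized linear model |
| Patient payments | not stated; inclusion implied by contrast | excluded |
| Difference from usual care | not stated | implied by net cost and change in claims costs |

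The list of cost inputs before the ratio covers treatment in every condition, but no sentence carries those inputs into the primary numerator.

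**2. How much the choice of numerator could matter**

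Inputs from the statistical power text in section 2.C4: six-month attempt risk p0 = 0.05; design odds ratios 0.89 (CC) and 0.87 (RRT). Section 2.C2 gives about 21,500 subscribers in the CC arm. Every dollar figure below is an assumption.

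Formula: p1 = odds × OR / (1 + odds × OR), where odds = 0.05/0.95 = 0.05263.

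- CC: 0.05263 × 0.89 = 0.04684, so p1 = 0.04475 and p0 − p1 = 0.00525. That is 1 attempt prevented per about 190 people mailed, or 21,500 × 0.00525 ≈ 113 in the arm.
- RRT: 0.05263 × 0.87 = 0.04579, so p1 = 0.04378 and p0 − p1 = 0.00622.

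Shift in the ratio = net care cost per subscriber / (p0 − p1). Arm size cancels. Results use unrounded risk differences.

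| Assumed net care cost per subscriber | CC | RRT |
|---|---|---|
| $10 | about $1,900 | about $1,600 |
| $50 | about $9,500 | about $8,000 |

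For CC, the net ratio is (program cost + induced care per person)/0.00525 − averted cost per attempt. With an assumed program cost of $6 per person:

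| Induced care per person | Averted cost per attempt | Program cost only | Net |
|---|---|---|---|
| $50 | $0 | $1,142 | $10,659 |
| $50 | $5,000 | $1,142 | $5,659 |
| $10 | $5,000 | $1,142 | −$1,955 |

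Over assumed ranges of $3 to $12 program cost, $0 to $50 induced care per person and $0 to $15,000 averted per attempt, the program-cost ratio runs from about $570 to $2,280. The net ratio runs from about −$14,400 to +$11,800, so the sign can change.

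**The case against.** A reader might infer that the plan deliberately uses gross program cost and leaves treatment payments out of the primary ratio. The documents do not support that. They never describe program cost as gross or as the only cost. The sentences before the ratio list treatment and co-pays as cost inputs. The statement that the MCO measure excludes patient payments makes sense only if the societal measure includes them, and patient payments arise from treatment, not from letters or training. This is good evidence that some treatment cost was meant to enter.

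Three further objections have force.

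- Induced and averted care paid by CareSource will be reported in the MCO analysis, and Aim 3 (section 2.A) promises savings and return on investment. The gap is therefore in the primary measure, not in the whole economic analysis.
- The dollar figures show sensitivity. They do not show that costs are omitted, or in which direction the ratio would err.
- A raw between-arm difference in payments would be a poor remedy. RRT is rolled out in a stepped wedge, so a raw difference is confounded with calendar time, and disenrolment shortens the period in which payments are seen.

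These points limit the claim and shape the remedy. They do not remove the problem. If a net numerator was intended, the formula does not say so and no societal cost-difference model is given. If program cost alone was intended, the label is wrong.

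**Conclusion.** The point holds as a mismatch between a stated formula and its label. The primary numerator is an undefined program cost which, taken at its word, is neither incremental to usual care nor net of care induced or averted. The text around it suggests that something wider was intended.

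Its size cannot be known from the documents. The shift of about $1,900 (CC) or $1,600 (RRT) per attempt prevented for each assumed $10 per subscriber rests on the plan's 0.05 risk and design odds ratios and is illustrative only. The direction of any error is unknown.

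The issue should be settled before analysis because it decides Aim 3's primary result. It does not touch the Aim 1 effectiveness tests.

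**What to change.** Amend the Aim 3 text as follows.

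1. **Define the numerator.** Program cost (mailings for CC, provider training for RRT) plus the adjusted intervention-versus-control difference in the payments the plan already tracks: CareSource payments plus co-pays and deductibles over the six months after release.
2. **Specify the model for that difference.** Match the Aim 1 design: indicators for CC, Study 2 inclusion and RRT, study month, agency-clustered errors, and days of MCO coverage. The MCO cost model cannot simply be reused, since its listed covariates omit study month and Study 2 inclusion. With a log link, convert the result to a dollar difference through model-based predicted means.
3. **Bootstrap numerator and denominator together.** Because the net numerator may be negative, also report the cost difference and the attempts prevented separately.
4. **Keep program cost per attempt prevented** as a named secondary figure.
5. **Match the label to the content.** Call it a health-care-sector perspective unless jail and other non-health costs are added. Jail days are to be extracted and returns to jail are an outcome, but the Aim 3 text puts no cost on them.

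The cost is a revised analysis section and one further model on data already planned. The numerator will carry sampling error, so the interval will be wider. Limiting it to the tracked mental health and suicide-related care avoids new extraction; a full societal measure would need jail unit costs that the documents do not describe.

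### The MCO cost model lists an undefined *treatments received* and no assigned-condition term, so it either adjusts for post-release care or codes exposure by receipt

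*Combined protocol and SAP*

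**What the plan says.** All of this is in the combined protocol and SAP, section C4 Data Analysis, in the paragraphs on Aim 3.

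- Purpose of the model: "Analyses from the MCO perspective will compute the change in claims costs by running a generalized linear model (GLM", with a log link and robust standard errors. On its form: "We will use a 2-part GLM unless less than 5% of patients have zero costs".
- Covariates: "Independent variables will include treatments received, demographics". The list then adds Elixhauser conditions and closes with "days of MCO coverage after jail discharge". Assigned CC, assigned RRT, Study 2 inclusion and study month are not in the list.
- The only other use of the phrase in Aim 3 is one paragraph earlier, where the plan describes what claims will capture: "Treatment received as part of the intervention and CAU conditions (including outpatient, inpatient, and ED mental health and suicide-related medical care visits".
- Cost definition: "Costs of CAU will be computed as CareSource payments plus co-pay and deductibles". The MCO view leaves out what patients pay.
- Primary cost-effectiveness measure: program cost over suicide attempts prevented. It is not described as using this model.

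Two neighbouring parts of C4 bear on the point. The Aim 1 model explicitly names indicators for Study 1 condition, Study 2 inclusion and Study 2 condition, and adjusts for study month. Aim 2 itself places post-release care on the causal path: "number of outpatient BH claims in the 6 months following the index jail release and number of calls to the CMS line as mediators".

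**The concern.** A model meant to give the change in claims cost caused by CC or RRT needs a term for the assigned condition, and its other terms should be fixed before randomisation or rollout. The listed model shows no assigned-condition term, and its first covariate can be read in two ways. Neither reading gives the intended contrast.

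If the phrase means post-release visits, the model holds constant the care through which CC and RRT are expected to act and which generates part of the outcome. A real saving or a real added cost arising through that care would then be reported as little or no difference. If the phrase means the study interventions received, the comparison is no longer by assignment, and the RRT part lacks the two terms that Aim 1 uses for the stepped-wedge comparison.

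Return on investment is part of Aim 3, and this is the only estimator described for the change in claims costs.

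**Working it through.** The documents give no cost, visit-rate or cost-effect figure for Aim 3, so there is no stated result to reproduce. The check takes each reading in turn.

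**Reading A: post-release visits.** Write cost as visits × price plus other claims. With a log link and a condition term A added to the listed covariates, the model is log E[cost | A, V] = b0 + b1·A + b2·V, where V is visits. Here b1 is the cost difference at equal visits, not the total difference. Without A there is no coefficient for the intervention at all.

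An illustrative simulation shows the consequence. Taken from the documents: 43,000 subscribers, half assigned to CC (C4, Statistical power). Assumed: a mean of 3 outpatient visits at about $150, a mean of 0.3 acute visits at about $3,000, and other claims of about $500 that the intervention does not change. Visit counts were Poisson with a person-level multiplier of mean 1. The model was a gamma GLM with log link and robust standard errors, with 12 replicates per scenario. Visits entered as log(1 + count).

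Control mean cost is 3 × 150 + 0.3 × 3,000 + 500 = 450 + 900 + 500 = 1,850.

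| Assumed effect | Expected ratio by arithmetic | Simulated, condition only | Simulated, condition plus visits |
|---|---|---|---|
| None | 1,850/1,850 = 1.000 | 1.005 | 1.003 |
| Outpatient +20% | (540+900+500)/1,850 = 1.049 | 1.046 | 0.998 |
| Acute −10% | (450+810+500)/1,850 = 0.951 | 0.951 | 1.004 |
| Acute −20% | (450+720+500)/1,850 = 0.903 | 0.900 | 1.000 |
| Outpatient +10%, acute −20% | (495+720+500)/1,850 = 0.927 | 0.922 | 1.008 |
| Outpatient +20%, acute −10% | (540+810+500)/1,850 = 1.000 | 1.004 | 1.003 |

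The condition-only model recovers the expected ratio to within about 0.005. Once visits are covariates, the estimate lies between 0.998 and 1.008 in every row, whatever the true ratio.

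**Reading B: CC or RRT received.**

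1. *Receipt is not assignment.* C2 (Caring Contacts fidelity) tracks returned letters, so CC could be coded by delivery. C2 (RRT Fidelity) says there is no scalable way to track outreach for the 6,000 Study 2 subscribers, so receipt of RRT outreach cannot be coded per person.
2. *Calendar time.* C2 starts the four agency cohorts at Months 4, 6, 8 and 10 of a 12-month period. Control months number 3 + 5 + 7 + 9 = 24 and RRT months 9 + 7 + 5 + 3 = 24, of 48 cohort-months. The control month numbers sum to 6 + 15 + 28 + 45 = 94, a mean of 94/24 = 3.9. The RRT months sum to 4 × 78 − 94 = 218, a mean of 218/24 = 9.1. Without study month, RRT and control differ by about five months of calendar time.
3. *Agency-client status.* Assume even releases and equal cohorts. Then 6,000 × 24/48 = 3,000 subscribers fall under RRT, all of them agency clients. The other 43,000 − 3,000 = 40,000 include only 3,000 agency clients, or 7.5%. Without Study 2 inclusion, RRT is compared mainly with people who were not recent clients of these agencies.

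**Other terms.** Days of coverage accrue after randomisation, and Aim 3 plans to track separation from the MCO by group, so they could differ by condition. Their role in the model is not stated. The time window for the Elixhauser conditions is not stated either, although C4 extracts both 12 months of pre-arrest and 6 months of post-release claims.

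**The case against.** A reader might infer that the plan itself defines the covariate as the post-release visits, and so is certain to adjust the cost effect away. The documents do not support that. The earlier paragraph describes what will be tracked in claims; it does not define a model term. C2 says participants may receive combinations of the two interventions, so the phrase could mean CC or RRT. A model for change in cost also needs an exposure term, and nothing else in the list could serve as one. The list is open-ended too, so a condition term may be intended. All of this stands, and it is why the point is put conditionally. It does not remove the need for an edit, because Reading B has its own defects.

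The illustration is open to a fair challenge. It adds a condition term that the plan does not list, and its inputs are assumed. It also leaves other claims unaffected by the intervention, so the pull toward 1 is partly built in. The visits described are mental health and suicide-related care, whereas claims cost carries no stated limit, and the Background reports chronic medical conditions in 47% of those jailed. Effects on other claims would not be fully removed. The table therefore shows a mechanism and is not an estimate for this trial.

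Two parts of the remedy are softer. C4 says under Aim 1 that all analyses covary past-year values of the dependent variable, which arguably already covers prior-year cost. Whether coverage days enter as an offset or a covariate is a modelling choice.

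**Conclusion.** The MCO-perspective cost model is under-specified in a way that matters under either reading. As visits, *treatments received* removes the part of the cost effect that runs through that care. As CC or RRT received, it replaces assignment with receipt, and the listed model leaves the RRT cost contrast confounded with agency-client status and calendar time.

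The size cannot be derived from the documents. Under the assumed inputs, true ratios of about 0.90 to 1.05 became about 1.00. The gap of about five months and the 7.5% figure depend only on the stated rollout and sample sizes, with even releases and equal cohorts assumed; they describe imbalance, not bias in dollars.

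The reach is limited to MCO cost and return on investment. A reader might extend it to all of Aim 3, but the primary cost-effectiveness ratio is not described as using this model.

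**What to change.** In the Aim 3 cost model:

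- Replace *treatments received* with the Aim 1 terms: assigned CC, Study 2 inclusion, RRT condition according to the assigned rollout, and study month.
- Restrict the remaining covariates to baseline: demographics, prior-year cost, and Elixhauser conditions taken from the 12 months before arrest.
- Leave post-release utilisation out of the total-cost model. If the cost pathway through care is of interest, report it as a separate mediation analysis.
- State the role of coverage days (exposure, offset or covariate) in each part of the two-part model, and acknowledge that they are measured after randomisation.

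This is a few lines of text. The data needed are already in the planned extraction, so the change adds no data collection and does not touch the primary ratio.
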